4.3.1.1. Costs

There are no costs to subjects for their participation in this trial.

4.3.1.2. Compensation

Subjects will be compensated for time and inconvenience in accordance with the standards for compensation of the NIH CC Clinical Research Volunteer Program. Compensation for a study visit that includes IV product administration is \$430; a study visit that includes SC product administration is \$375. If enrollment occurs on a different day than study product administration, then visit compensation will be \$85. Compensation will be \$200 for scheduled follow-up visits that include venipuncture, \$85 for clinic visits that do not include venipuncture, and \$25 for timely completion of all 7 days of the electronic diary card. The total amount of compensation varies depending upon the group and the visits completed.

4.3.2. Screening

All screening procedures for this study are described and will be completed through the Vaccine Research Center's screening protocol, VRC 500 (NIH 11-I-0164) used for all VRC IND studies conducted at the NIH Clinical Center. The Recruitment Plan per NIH Policy 302 for all VRC studies can be found in the NIH IRB approved VRC 500 protocol. Subjects will be recruited through Institutional Review Board (IRB)-approved advertising. Screening evaluations performed to determine eligibility for study participation will include medical history review, physical exam, and the clinical laboratory tests as detailed in the Schedule of Evaluations, [Appendix I](#)). No screening procedures will be done under protocol VRC 615.

Additional assessments of health may be conducted at screening based on clinical judgment. Screening evaluations for specific eligibility criteria must be completed within the time interval specified prior to enrollment for the given parameter and may be repeated, as needed, to confirm eligibility.

Blood samples for research can be drawn at any time during the screening period and are not subject to a time interval. Informed consent documents will be reviewed. Counseling related to potential risks of the study product, pregnancy prevention, and HIV risk-reduction will be performed. An Assessment of Understanding (AoU) will be completed in association with enrollment into VRC 615. Screening records will be maintained to document the reason why an individual was screened but not enrolled.

Subjects who are not up to date on standard vaccinations may receive these, if available, during their participation in the screening protocol or at a later date during study participation as described in [Sections 4.3.4](#) and [4.3.9](#).

4.3.3. Enrollment, Study Days and Visit Numbers

In this study, enrollment is defined as the assignment of a study identification number and study group schedule in the clinical database. A clinician will discuss the target dates and timing of the study product administration(s) and sample collections before completing an enrollment to help ensure that the subject can comply with the projected schedule. Informed consent must be obtained prior to enrollment.

Day 0 is defined as the day of first VRC01.23LS administration. Day 0 may occur on the same day as enrollment or up to 6 weeks after enrollment. This period may be increased with PI approval. If Day 0 does not coincide with enrollment, then the enrollment day may be referred to by a negative number of days (i.e., Day -1 to Day -42). For calculating elapsed days following Day 0, each subsequent calendar date is labeled by the next sequential “Study Day” as shown in the Schedule of Evaluations ([Appendix I](#)). Since there may be more than one research sampling timepoint of interest per study day, each sample collection timepoint has its own “Visit Number.” For this reason, there may be more than one visit number recorded on the same calendar date.

Medical history and Day 0 evaluations prior to the first study product administration are the baseline for subsequent safety assessments.

4.3.4. Administration of VRC01.23LS

All study product administrations will be completed according to the assigned group. Licensed vaccines should be avoided within 2 weeks before and after product administration. Prior to administering study product, a clinician should consult with an advanced practitioner if licensed vaccination occurred or is scheduled within that time frame.

On the day of and prior to each product administration, vital signs (temperature, blood pressure, heart rate and respiratory rate), and weight will be recorded, a targeted physical examination may be conducted as needed, and women of childbearing potential must have a negative pregnancy test.

4.3.4.1. IV Administration

If a subject is assigned to an IV administration group, the IV access will be placed in an arm vein in an aseptic manner. A different site may be used for collection of PK blood samples; however, the same site may be used after flushing the line if another site is not available. VRC01.23LS will be administered with approximately 100 mL of normal saline IV over about 15-30 minutes, with a target of 30 minutes. Infusions lasting longer than 30 minutes are allowed. If the subject experiences side effects during the infusion, the rate of infusion may be slowed or stopped to alleviate the symptoms. At the end of product administration, the IV administration set must be flushed with about 30 mL (or appropriate volume) of normal saline under the same infusion rate to ensure the entire dose is given.

4.3.4.2. SC Administration

If a subject is assigned to a SC administration group, the SC administration site(s) to be used must be assessed as acceptable by the clinician and the subject. The preferred SC administration site is the abdomen, but the upper arm or thigh may be used. Given the weight criterion in this study, the maximum volume needed to administer a 5 mg/kg SC dose is not expected to exceed 5.75 mL. The SC dose will be administered by standard needle in a maximum volume of about 2.5 mL per injection site. Up to three (3) SC injection sites may be used if deemed necessary by the clinician. SC administration sites should be at least 2 inches apart.

4.3.5. Post-Product Administration Follow-up

Following completion of IV product administration in Groups 1, 3, 4, and 6, subjects will be observed for at least 2 hours in the clinic. Following completion of SC product administration in Groups 2 and 5, subjects will be observed for at least 1 hour in the clinic.

Prior to discharge from the clinic, subjects will be assessed for local and systemic reactogenicity, and vital signs will be recorded. Any subject who is assessed as being unwell or has ongoing reactogenicity symptoms will be asked to remain in the clinic until evaluation and discharge by a study clinician. This includes the possibility of an overnight inpatient stay to evaluate for safety.

4.3.6. Solicited Adverse Events and Clinical Follow-up

Each subject will be given a 7-day diary (paper and electronic-based available), a thermometer, and a measuring tool. The subjects will use the diary to record their highest temperature, local and systemic symptoms, and concomitant medications taken for 7 days after any product administration. Subjects will be provided training on diary completion and proper usage of the thermometer to measure temperature and the measuring device to measure injection site reactogenicity. Completion of diary card training will be noted in the source documents. The web-based diary for this study is entered in the electronic database provided by Emmes Corporation via a NIAID approved contractual agreement. No personal identifiable information (PII) is entered in this database. The secure web-based electronic method is preferred for diary completion, but subjects will have the option to use a paper diary. The paper diary, if used, will be transcribed into the study database and stored in the subject file for monitoring purposes. When neither paper nor electronic diary is available from the subject, the study clinician will document the source of reactogenicity information recorded in the study database.

The signs and symptoms solicited by diary will include systemic events of temperature, feeling unusually tired/unwell, muscles aches (outside the injection site), headache, chills, nausea and joint pain; and local event at the product administration site of pain/tenderness, swelling, redness, bruising, and pruritus. Subjects will record their highest measured temperature daily for assessment of fever and largest measured diameter of redness, swelling, and bruising at the injection site, if applicable. Subject diaries will be reviewed by a clinician for accuracy and completeness at follow-up visits. Clinicians will follow and collect resolution information for any reactogenicity symptoms that are not resolved within 7 days.

Diary card data will be available in real-time for subjects who use the electronic diary. Subjects using a paper diary will be encouraged to contact the clinic as soon as possible for any moderate or severe side effects that they experience in the 7 days post product administration. A clinician may contact the subject by phone if any moderate or severe side effect is reported. Events that may require a clinic visit include rash, urticaria, fever of 38.6°C (Grade 2) or higher lasting greater than 24 hours, or significant impairment in the activities of daily living (ADL) (such as those consistent with Grade 2 or higher impairment). Additionally, other clinical concerns may prompt a study visit based on the judgment of a study clinician.

Clinical laboratory assays and clinical evaluations will assess safety and tolerability at specified intervals after each administration. Throughout the study, clinicians will also assess subjects for any changes in symptoms. Any new or concerning symptoms will be fully assessed to include specialty consultation at the NIH Clinical Center as indicated clinically.

4.3.7. Pharmacokinetics

PK samples will be collected as close as reasonably possible to the target timepoints. However, actual time of collection is critical for PK analysis and will be recorded for all samples. The PK timepoints are shown in the Schedule of Evaluations ([Appendix I](#)).

4.3.8. Follow-Up through End of Study

The Schedule of Evaluations ([Appendix I](#)) provides details on the study schedule and the allowable windows for completing study visits. Study follow-up will continue via clinical visits through 24 weeks after the final product administration. The visit schedule is based on intervals of time after product administration. Out of window study visits will be discouraged and recorded as protocol deviations but may be permitted at the discretion of the PI in the interest of obtaining safety and PK evaluations following exposure to the investigational study product.

Any subject who receives investigational product will be required to follow the product administration schedule for a complete safety and research evaluation through study duration.

If product administration is discontinued for a Group 5 or 6 subject assigned to receive repeat product administrations, then the study schedule may be modified, and the subject will be followed for 24 weeks after the last product administration received. Schedule 5 of the SOE outlines this altered schedule. Briefly, subjects will be followed according to the assigned group visit schedule until the 12th week after their last product administration and will then complete the protocol according to [Schedule 5](#) starting at Visit 11 for those who receive only one product administration or Visit 17 for those who receive two product administrations.

Additional visits and blood draws may be scheduled during the study if needed to assess subject safety or for sample collection for immunological testing. Any evaluation for an AE or possible exacerbation of a pre-existing condition may be evaluated at study team discretion as a “protocol related” evaluation.

After study completion, subjects may be invited to participate in one of the VRC sample collection protocols (VRC 200 or VRC 900) for follow-up sample collection.

4.3.9. Concomitant Medications

Only routine prescription medications will be entered in the database at the time of enrollment. Subsequently, concomitant medications are only updated or recorded in the study database if there is an occurrence of an adverse event (AE) that requires expedited reporting, a change to pre-existing condition treatment, or the development of a new chronic condition that requires ongoing medical management. Receipt of an FDA-approved vaccine at any time during the study will be recorded in the database. Clinicians should work with subjects regarding the timing of licensed vaccines relative to study product administration as indicated in [4.3.4](#). Otherwise, concomitant medication changes throughout the study will be recorded in the subject’s chart as needed for general medical documentation but will not be recorded in the database.

4.4. Criteria for Dose-Escalation

This study will include a series of interim safety reviews to assess product safety in a stepwise manner. The activation of additional dose groups will proceed in a staged manner that is governed by the outcome of the planned interim PSRT data reviews. The PSRT must assess the data as showing no significant safety concerns before proceeding with group activation.

Table 3: Plan for Dose-Escalation Reviews

Data Review Objective	Minimum Evaluable Safety Data*	Favorable Review Outcome
Review #1		
• Dose-escalation from 5 to 20 mg/kg IV	• All post-administration safety data from Day 0 through at least the “Day 7” visit in at least 3 5-mg/kg IV recipients from Group 1.	• Proceed with enrollment into Groups 3 and 6.
Review #2		
• Dose-escalation from 20 to 40 mg/kg IV	• All post-administration safety data from Day 0 through at least the “Day 7” visit in at least 3 20 mg/kg IV recipients from Groups 3 or 6.	• Proceed with enrollment into Group 4.

Group 2 and Group 5 enrollment (5 mg/kg SC) does not depend on dose-escalation reviews for the IV doses.

If there are discontinuations from the study before there are sufficient data to conduct the dose-escalation review, then additional subjects may be enrolled to have the requisite data on at least 3 subjects at the dose level and route being evaluated. Additionally, AEs assessed as related to the study product at the time of a dose-escalation review may be judged by the PSRT to warrant adding additional subjects to a particular group. Consultation with the IRB or FDA as per study pause criteria may occur if indicated.

4.5. Criteria for Subject Discontinuation from Protocol Participation

Subjects who receive at least one dose of VRC01.23LS will be encouraged to stay on the study and complete safety evaluations. A subject may be discontinued from protocol participation for the following reasons:

- Subject voluntarily withdraws;
- Pregnancy;
- The IND Sponsor or regulatory authorities stop the study;
- The PI assesses that it is not in the best interest of the subject to continue participation in the study; or
- Severe non-compliance as determined by the PI.

4.6. Criteria for Discontinuation of VRC01.23LS Administration

Under certain circumstances, a subject may be prohibited from receiving further study product administrations. These include:

- Grade 3 adverse event assessed as related to VRC01.23LS (with the exception of self-limited Grade 3 solicited reactogenicity that resolve during the solicited reactogenicity period);
- Grade 4 adverse event assessed as related to VRC01.23LS;
- SAE assessed as related to VRC01.23LS;
- Immediate hypersensitivity reaction associated with VRC01.23LS;
- Intercurrent illness that is not expected to resolve prior to the next scheduled study product administration and for which PI (or designee) believes is in the best interest of the subject to restrict further exposure;
- Repeated failure to comply with protocol requirements.

Subjects who receive at least one dose of VRC01.23LS but are discontinued from further study product administrations will continue with follow-up as shown in the Schedule 5 of the Schedule of Evaluations with the exception that research sample collections will be discontinued for pregnant women or others in which it is contraindicated.

4.7. Criteria for Pausing and Resuming the Study

The study team will closely monitor and review study data as they become available to make determinations regarding the presence and severity of adverse events (AEs). Study product administrations and new enrollments will be paused if any of the following criteria are met:

- **One** (or more) subject experiences a serious adverse event (SAE) that is assessed as related (possible, probably, or definitely) to the study product, or
- **Two** (or more) subjects experience the same **Grade 3 or higher AE** that is assessed as related (possible, probably, or definitely) to study agent (other than self-limited Grade 3 AEs that resolve during the solicited reactogenicity period).

In the event of a pause, the IND Sponsor Medical Officer (MO) and the PSRT will be promptly notified.

Plan for Review of Pauses and Resuming Rules:

Study product administration and enrollments would resume only if review of the AEs that caused the pause results in a recommendation to permit further study product administrations and study enrollments. The reviews to make this decision will occur as follows:

- **Pauses for related SAEs:** The IND Sponsor Medical Officer (MO), with participation by the PI, will conduct the review and make the decision to resume, amend or close the study. The IRB and FDA will be notified accordingly.
- **Pauses for Grade 3 or higher related AEs:** The IND Sponsor MO, in consultation with the PI, will conduct the review and make the decision to resume, amend or close

the study for the Grade 3 or higher AEs that meet criteria for pausing the study. As part of the pause review, the reviewers will also advise on whether the study needs to be paused again for any subsequent events of the same type. The FDA and the IRB will be notified of Grade 3 or higher pause reviews and of the IND Sponsor's decisions.

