1.3.2. VRC01LS

VRC HIV-1 human bnAb VRC01LS, the parent of VRC01.23LS, has been evaluated in five clinical trials. As of August 30, 2021, 112 subjects have received one or more doses of VRC01LS. VRC01LS IV and SC administrations have been well-tolerated in adults and children; there have been no SAEs related to VRC01LS. Clinical information regarding VRC01LS is available under DAIDS IND 125494 (VRC 606, HVTN 116), DAIDS IND 140909 (Dual bnAb protocol), DAIDS IND 130804 (VRC 607), and in Gaudinski et al [26].

In the three prevention studies (VRC 606, HVTN 116, and P1112), 56 healthy adults and 21 HIV-exposed infants have received VRC01LS in doses ranging from 5 to 40 mg/kg IV and 5 mg/kg SC in adults and up to 100 mg/dose SC in infants. VRC 606, a VRC01LS phase I dose escalation study, has been completed and results published [26] (NCT02599896). HVTN 116, a phase I study to evaluate VRC01LS and VRC01 safety, tolerability, PK, and anti-viral activity in healthy adults has also been completed (NCT02797171). A phase I study, IMPAACT P1112, evaluating the safety and PK of VRC01, VRC01LS, or another CD4bs mAb, VRC07-523LS, in HIV-1 exposed infants, has completed investigational product (IP) administration (NCT02256631).

In the two therapeutic studies in HIV-positive subjects (VRC 607 and Dual bnAb treatment in children), seven HIV-viremic adults and 28 HIV-suppressed children have received VRC01LS at doses ranging from 10 to 40 mg/kg IV. VRC 607/A5378, a phase I single dose study evaluating the safety and anti-viral effect of VRC01LS and VRC07-523LS in HIV-infected viremic adults, has been completed (NCT02840474). VRC01LS continues to be studied in HIV-infected, virally suppressed children in a Phase1/2 study (Dual bnAb), administering VRC01LS and mAb 10-1074 (NCT03707977).

Collectively, safety data from these studies indicate that VRC01LS is safe and well tolerated at doses ranging from 5 mg/kg to 40 mg/kg. The overall safety profile is consistent with expected events for monoclonal antibodies, most commonly mild to moderate reactogenicity that occurs shortly after product administration and is self-limited. There have been no unexpected safety trends identified and no SAEs related to VRC01LS.

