8.2. Risk/Benefit Assessment

8.2.1. Potential Risks

Risks of VRC01.23LS and mAb Administration

The side effects of mAbs are mild but may include reactions at the injection site (pain, redness, bruising, swelling), fever, chills, rigors, nausea, vomiting, pain, headache, dizziness, shortness of breath, bronchospasm, hypotension, hypertension, pruritus, rash, urticaria, angioedema, diarrhea, tachycardia or chest pain. Clinical use of mAbs that are targeted to cytokines or antigens associated with human cells may be associated with an increased risk of infections [\[41\]](#); however, this is not expected to be a risk for a mAb targeted to a viral antigen.

Administration of mAbs may cause immune reactions such as acute anaphylaxis, serum sickness, and the generation of antibodies. However, these reactions are rare and more often associated with mAb targeted to human proteins or with the use of murine monoclonal antibodies which would have a risk of human anti-mouse antibodies [\[41\]](#). It is expected that that VRC01.23LS

will have a low risk of such side effects since it is directed against a viral antigen and is human in origin.

Published experience with other human mAb directed against cell surface targets on lymphocytes have shown that infusion of a mAb may be associated with cytokine release, causing a reaction known as “cytokine release syndrome” (CRS) [42]. Most infusion-related events occur within the first 24 hours after beginning administration. Severe reactions, such as anaphylaxis, angioedema, bronchospasm, hypotension and hypoxia, are infrequent and more often associated with mAbs targeted to human proteins or when a non-human mAb, such as a murine mAb, is used [41]. Specifically, with regard to the rare CRS reactions, these generally occur within the first few hours of beginning the infusion and are more common with the first mAb infusion received. This is because the cytokine release is associated with lysis of the cells targeted by the mAb and the burden of target cells is greatest at the time of the first mAb treatment. With licensed therapeutic mAbs, CRS is managed by temporarily stopping the infusion, administration of histamine blockers, and restarting the infusion at a slower rate [43].

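### The 4.7 pause rule exempts unsolicited as well as solicited self-limited Grade 3 events, unlike the stopping rule in 4.6, so a repeated event of this kind does not force a pause

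*Combined protocol and SAP*

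**What the plan says.** Section 4.7 gives two conditions that stop dosing and enrollment. The first is one related SAE. The second is the same related AE of Grade 3 or higher in two or more subjects, "other than self-limited Grade 3 AEs that resolve during the solicited reactogenicity period".

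Section 4.6 lists the grounds on which "a subject may be prohibited from receiving further study product administrations". A related Grade 3 AE is one of them, "with the exception of self-limited Grade 3 solicited reactogenicity that resolve during the solicited reactogenicity period". Related Grade 4 events, related SAEs and immediate hypersensitivity reactions are listed with no such exception.

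Section 4.3.6 defines what is solicited, over 7 days after each administration: "The signs and symptoms solicited by diary will include systemic events of temperature, feeling unusually tired/unwell, muscles aches (outside the injection site), headache, chills", then "nausea and joint pain; and local event at the product administration site of pain/tenderness, swelling, redness, bruising, and pruritus". Section 5.1 defines solicited AEs by reference to that list and records them without attribution. Unsolicited AEs are a separate class, recorded with attribution through the Day 28 visit.

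Section 8.2.1 names possible systemic side effects of monoclonal antibodies: "fever, chills, rigors, nausea, vomiting, pain, headache, dizziness, shortness of breath, bronchospasm, hypotension, hypertension, pruritus, rash, urticaria, angioedema, diarrhea, tachycardia or chest pain".

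**The concern.** The two rules share a time window but exempt different sets of events. In 4.6 the word 'solicited' describes both the event and the window. In 4.7 it describes only the window, so any AE qualifies, including the unsolicited reactions that the diary does not ask about. The documents do not explain the difference, and no other section narrows 4.7.

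This is a first-in-human trial, and 4.7 is the only rule that turns a count of events into a mandatory pause. If it does not count a class of related Grade 3 reactions, the response to a second case rests on judgment. The notification of FDA and the IRB that 4.7 attaches to Grade 3 pause reviews does not arise either.

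**Working it through.** **Step 1. The two exceptions side by side.**

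| Feature | 4.6, individual stop | 4.7, study pause |
|---|---|---|
| Grade exempted | 3 | 3 |
| Must be self-limited | yes | yes |
| Must resolve in the solicited period | yes | yes |
| Must be solicited reactogenicity | yes | no |
| Effect if not exempt | subject may lose later doses | study must pause at the second subject |

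**Step 2. One case through each rule.** Take two subjects with urticaria that is related, Grade 3, non-serious, self-limited and resolved within 7 days. Urticaria is not on the 4.3.6 diary list, so it is unsolicited.

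- 4.7, SAE condition: not met, because the event is non-serious.
- 4.7, two-subject condition: not met, because the parenthesis removes both events.
- 4.6: the exception does not apply, so further doses may be withheld. This matters only where a dose remains, that is in Groups 5 and 6 after dose 1 or 2: 5 + 5 = 10 of 22 planned subjects. The other 4 × 3 = 12 receive one dose only.
- 4.4: the PSRT must judge the safety data through at least the Day 7 visit acceptable before 20 and 40 mg/kg IV open. This does not gate the SC groups, doses 2 and 3, or dosing after Group 4 opens.
- 8.9: the daily and weekly reviews would see both events, but no event count is attached to them.
- 9.1: suspension is permitted, not required.

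**Step 3. Which named reactions are off the diary.** Section 8.2.1 names 19 systemic terms. On a generous match (rigors to chills, pain to muscle or joint pain, pruritus to local pruritus), 7 are on the diary: fever, chills, rigors, nausea, pain, headache and pruritus. The other 19 − 7 = 12 are vomiting, dizziness, shortness of breath, bronchospasm, hypotension, hypertension, rash, urticaria, angioedema, diarrhea, tachycardia and chest pain. This counts names only. It does not show that each can be Grade 3, non-serious and self-limited.

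**Step 4. Probability that two or more subjects have the event.** The formula is P(2+) = 1 − (1 − p)^n − n·p·(1 − p)^(n−1).

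The protocol gives no operating characteristic for the pause rule. The nearest figures are the Pr(2+ events) columns of Table 4, and they reproduce:

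- n = 3, p = 0.10: 1 − 0.729 − 0.243 = 0.028 (Table 4: 0.028).
- n = 5, p = 0.10: 1 − 0.5905 − 0.3281 = 0.081 (Table 4: 0.081).

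The 4.7 count runs across the study, so the relevant n is the planned 22, or up to the permitted 40. The true rate p per subject is an assumption.

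| Assumed p | Pause forced, current text | With 4.6 wording, n = 22 | With 4.6 wording, n = 40 |
|---|---|---|---|
| 0.01 | 0 | 0.020 | 0.061 |
| 0.05 | 0 | 0.302 | 0.601 |
| 0.10 | 0 | 0.661 | 0.920 |
| 0.20 | 0 | 0.952 | 0.999 |

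The zeros follow from the wording and hold at any p.

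**The case against.** The strongest reply is that the rules need not match. Section 4.6 governs re-dosing of one person and 4.7 halts a trial, so a wider exemption for brief, self-resolving events could be a deliberate study-level choice. That is possible, but the protocol does not say so.

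Several narrower objections stand and limit the point:

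- The exemption covers self-limited events, not all transient ones. The term is undefined. A reaction that resolved only with treatment can reasonably be read as outside it, and 8.2.1 describes managing reactions by stopping or slowing the infusion, histamine blockers and supportive care. Hypotension, bronchospasm or angioedema may therefore often still count.
- Serious events are not exempt. Section 5.2 includes important medical events and gives treated allergic bronchospasm as an example, so one such related event pauses the study.
- The events would not go unseen. Section 8.9 requires daily and weekly review, and 4.3.6 names rash and urticaria among events that may prompt a clinic visit.
- They are likely to be uncommon. Section 8.2.1 says "Severe reactions, such as anaphylaxis, angioedema, bronchospasm, hypotension and hypoxia, are infrequent", and 1.3.2 describes VRC01LS events as "most commonly mild to moderate reactogenicity that occurs shortly after product administration and is self-limited".

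A reader might infer that the study could continue unchecked through repeated severe hypersensitivity, or that 12 of 19 named reactions escape the pause rule. The documents support neither. The first overlooks the SAE and Grade 4 routes and the reviews. The second treats a count of terms as a measure of risk.

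**Conclusion.** The point holds in a limited form. One class of event, namely related, non-serious, self-limited, unsolicited Grade 3 AEs that resolve in the 7-day period, does not count toward the two-subject pause, however many subjects have it. Sections 4.4, 4.6, 8.9 and 9.1 let the team respond, but none obliges it to pause at a second case.

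The gap has no size in expected events, because the documents give no rate. The probabilities assume independent subjects with a common rate, and that all 22 or 40 are dosed. They show what the wording change does at each assumed rate and do not predict events. If severe reactions are as infrequent as 8.2.1 suggests, the low end of the range is the more relevant. The mismatch between the two sections is certain. Its practical consequence is probably small, and the case for acting rests mainly on the low cost of correction.

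**What to change.** In the 4.7 parenthesis, replace 'AEs' with 'solicited reactogenicity' (and 'resolve' with 'resolves'), so that the exemption matches 4.6. If the wider exemption was intended, state that and give the reason.

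The edit adds no visits, samples or analyses. The cost is an occasional extra, reversible pause. Unsolicited AEs include laboratory AEs, so the same brief, related Grade 3 laboratory AE in two subjects would also stop dosing and enrollment. Each such pause brings a sponsor medical officer review and notification of FDA and the IRB. It could also push a Week 12 or Week 24 dose in Groups 5 and 6 outside its ±7-day window.
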